Appendix C: 2018 Guideline on the Management of Blood Cholesterol

Top Ten Things to Know 2018 Guideline on the Management of Blood Cholesterol

- In all individuals, emphasize a heart-healthy lifestyle across the life course.
- In patients with clinical atherosclerotic cardiovascular disease (ASCVD), reduce low-density lipoprotein cholesterol (LDL-C) with high-intensity statin therapy or maximally tolerated statin therapy.
- In very high-risk ASCVD, use an LDL-C threshold of 70 mg/dL (1.8 mmol/L) to consider addition of non-statins to statin therapy.
- In patients with severe primary hypercholesterolemia (LDL-C level ≥190 mg/dL (≥4.9 mmol/L)), begin high-intensity statin therapy without calculating 10-year ASCVD risk.
- In patients 40 to 75 years of age with diabetes mellitus and an LDL-C level of ≥70 mg/dL (≥1.8 mmol/L), start moderate-intensity statins without calculating 10-year ASCVD risk.
- In adults 40 to 75 years of age evaluated for primary ASCVD prevention, have a clinician-patient risk discussion before starting statin therapy.
- In adults 40 to 75 years of age without diabetes mellitus and with LDL-C levels ≥70 mg/dL (≥1.8 mmol/L), at a 10-year ASCVD risk of ≥7.5%, start a moderate-intensity statin if a discussion of treatment options favors statin therapy.
- In adults 40 to 75 years of age without diabetes mellitus and 10-year risk of 7.5%-19.9%, riskenhancing factors favor initiation of statin therapy.
- In adults 40 to 75 years of age without diabetes mellitus and with LDL-C levels ≥70 mg/dL-189 mg/dL (≥1.8-4.9 mmol/L), at a 10-year ASCVD risk of ≥7.5%-19.9%, if a decision about statin therapy is uncertain, consider measuring coronary artery calcium (CAC).
- Assess adherence and percentage response to LDL-C-lowering medications and lifestyle changes with repeat lipid measurement 4 to 12 weeks after statin initiation or dose adjustment, repeated every 3 to 12 months as needed.

Other highlights:

- For secondary prevention, at mid-2018 list prices PCSK9 inhibitors have a low-cost value
 [>\$150,000 per QALY (quality-adjusted life-year)] compared to good cost value [<\$50,000 per
 QALY]. The guideline provides a full discussion of the dynamic interaction of different prices and
 clinical benefit.
- 2. This guideline provides recommendations for children and adolescents with lipid abnormalities.
- Substantial advances in estimation of risk with CAC scoring have been made in the past 5 years.
 One purpose of CAC scoring is to reclassify risk identification of patients who will potentially benefit from statin therapy. This is especially useful when the clinician and patient are uncertain whether to start a statin.

AHA/ACC/AACVPR/AAPA/ABC/ACPM/ADA/AGS/APhA/ASPC/NLA/PCNA guideline on the management of blood cholesterol: a report of the American College of Cardiology/American Heart Association Task Force on Clinical Practice Guidelines [published online ahead of print November 10, 2018]. *Circulation*. DOI: 10.1161/CIR.0000000000000625.

# **VERSION HISTORY**

Version	/ersion Version Date Description		
1.0	1.0 09 July 2019 Original signed version		
2.0	19 February 2020	Updated per Amendment 1 and Amendment 2	

# LIST OF ABBREVIATIONS

Abbreviation	Definition		
ADA	Antidrug antibody		
AE	Adverse event		
AESI	Adverse event of special interest		
ATC	Anatomical therapeutic chemical		
ALP	Alkaline phosphatase		
ALT	Alanine aminotransferase		
ANCOVA	Analysis of covariance		
AST	Aspartate aminotransferase		
AUC	Area under the plasma concentration-time curve		
AUC 0-∞	Area under the plasma concentration-time curve from time 0 extrapolated to infinity		
AUC 0-24	Area under the plasma concentration-time curve from time 0 to 24 hours		
AUC 0-48	Area under the plasma concentration-time curve from time 0 to 48 hours		
AUC 0-168	Area under the plasma concentration-time curve from time 0 to 168 hours		
AUC 0-t	Area under the plasma concentration-time curve from time 0 to the time of last quantifiable concentration		
AUC extrap	Extrapolation of area under plasma concentration		
BLQ	Below the lower limit of quantification		
BMI	Body mass index		
CRF	Case report form		
CL/F	Apparent clearance		
CSR	Clinical Study Report		
C max	Maximum observed plasma concentration		
C trough	Concentration observed at pre-dose		
CTCAE	Common Terminology Criteria for Adverse Events		
Ecrf	Electronic Case Report Form		
HbA1c	Hemoglobin A1c		
HDL-C	High-density lipoprotein cholesterol		
hsCRP	High-sensitivity C-reactive protein		
ITT	Intent-to-treat		
LDL	Low-density lipoprotein		
LDL-C	Low-density lipoprotein cholesterol		
LLOQ	Lower limit of quantitation		
MedDRA	Medical Dictionary for Regulatory Activities		
MMRM	Mixed-Effect Model Repeated Measure		
NCA	Non-compartmental analyses		
PCSK9	Proprotein convertase subtilisin/kexin type 9		
PD	Pharmacodynamic(s)		
PK	Pharmacokinetic(s)		
PP	Per-Protocol		
Q4W	Every 4 weeks		
SAE	Serious adverse event		
SAP	Statistical Analysis Plan		

Abbreviation	Definition	
SC	Subcutaneous(ly)	
SD	Standard deviation	
SRC	Safety Review Committee	
TEAE	Treatment-emergent adverse event	
TG	Triglyceride	
TSH	Thyroid-stimulating hormone	
ULN	Upper limit of normal	
VLDL	Very low density lipoprotein	
VLDL-C	Very low density lipoprotein-Cholesterol	
V z /F	Apparent volume of distribution during the terminal phase	
WHO	World Health Organization	

#### 1 INTRODUCTION

The purpose of this Statistical Analysis Plan (SAP) is to provide a description of the statistical methods and pharmacokinetic (PK) methodology to be implemented for the analysis of data from the study with CiVi Biopharma, Inc. protocol number CIVI 007-2-01. The SAP will be finalized prior to database lock. Any deviations from the SAP after database lock will be substantiated by sound statistical/PK rationale and will be documented in the final Clinical Study Report (CSR).

#### 2 STUDY OVERVIEW

# 2.1 Study Objectives

## 2.1.1 Primary Objective

The primary objective of the study is to assess the safety and tolerability of CIVI 007 following multiple subcutaneous (SC) doses in patients on a background of a stable dose of statin therapy.

## 2.1.2 Secondary Objectives

The secondary objective is to assess the pharmacodynamic (PD) effect of CIVI 007 on total plasma proprotein convertase subtilisin/kexin type 9 (PCSK9) and low-density lipoprotein cholesterol (LDL-C) levels in the study population.

# 2.1.3 Exploratory Objectives

The exploratory objectives include the following:

- To assess the effect of CIVI 007 on other lipid and lipoproteins including triglycerides (TG), high density lipoprotein cholesterol (HDL-C), non-HDL-C, very low-density lipoprotein cholesterol (VLDL-C), total cholesterol, apolipoproteins B, A-I and lipoprotein(a)
- To assess the effect of CIVI 007 on high-sensitivity C-reactive protein (hsCRP)
- To collect antidrug antibody (ADA) samples for potential future assessments of immunogenicity
- To further inform the population pharmacokinetic (PK) model of CIVI 007 with sparse PK sampling in patients on a background of statin therapy

# 2.2 Study Design

#### 2.2.1 Overview

This is a Phase 2a, randomized, double-blind (investigator/subject), sponsor-open, parallel-group, multicenter study to evaluate the early clinical profile (safety, tolerability, pharmacodynamics and pharmacokinetics) of CIVI 007 in patients on a background of statin therapy with or without ezetimibe. Patients are required to be on standard of care treatment for high blood cholesterol consistent with 2018 ACC/AHA guidelines that includes a stable dose of statin therapy (with or without ezetimibe) for at least 4 weeks prior to the Screening Visit. The study will enroll approximately 48 patients who will be randomized to 1 of 3 active treatment groups or the placebo reference group (12 patients per active treatment group and 12 in the placebo treatment group) across approximately 7 sites in the United States.

All potentially eligible patients will partake in the Screening Visit up to 21 days prior to Day 1. The Screening Visit will be their first study visit. Laboratory values can be retested once during screening for LDL-C that is in the range of 65-69 mg/dL, or for triglycerides in the range of 401-450 mg/dL.

[figure not shown]
The Treatment Period will be approximately 28 days from Day 1 to Day 29; each treatment group will receive 2 administrations of study drug. Eligible patients will be randomized on Day 1 in a 1:1:1:1 ratio to one of the following treatment groups:

- Group 1: mg CIVI 007 administered SC on Days 1 and 29
- Group 2: mg CIVI 007 administered SC on Day 1 followed by mg CIVI 007 administered SC on Day 29
- Group 3: mg CIVI 007 administered SC on Days 1 and 29
- Group 4: Placebo for CIVI 007 administered SC on Days 1 and 29

The Follow-up Period will be approximately 8 weeks and begin following the last dose of study drug, unless extended follow-up is required based on the Day 85 LDL-C assessment or other Investigator determined safety considerations.

Extended follow-up visits will be conducted on a monthly basis for up to 3 months if Day 85 LDL-C levels are <80% of their baseline level; extended follow-up will end within the 3-month period if LDL-C levels are ≥80% of baseline. Extended follow-up visits (frequency and assessments will be at the discretion of the Investigator) to monitor Investigator determined safety considerations may extend beyond 3 months, if deemed appropriate by the Investigator, and will continue until there are no safety observations requiring further follow-up. The total duration of the study for each patient will be approximately 3 to 6.5 months, depending on the length of the screening, and follow up periods.

The study design is graphically summarized below:

Patients will be routinely monitored for safety, tolerability and pharmacodynamic effects. The schedule of procedures and clinical laboratory analytes are detailed in Appendices of the protocol: measurements will be taken as detailed in Appendix A (schedule) and Appendix B (clinical laboratory analytes).

CiVi Biopharma, Inc. Protocol: CIVI 007-2-01

#### 2.2.2 Randomization and Blinding

Approximately 48 patients will be assigned randomly to placebo, or mg CIVI 007, or mg CIVI 007 in a 1:1:1:1 allocation ratio.

Throughout the study, study treatment will be administered in a double-blinded fashion for the Investigator, clinical staff and patients. Only where required will key site staff (such as pharmacist) be unblinded throughout the study.

The following controls will be employed to maintain the double-blind execution of the study:

- The placebo solution will be identical in appearance to the CIVI 007 solution.
- The Investigator and other members of staff involved with the study will remain blinded.
- Lipid levels after randomization will be blinded to the study site.
- Appropriate firewalls will exist to prevent communication between the unblinded SRC and personnel involved in study execution.

# 2.2.3 Study Drug

CIVI 007 and placebo are sterile solutions to be administered by SC injection. Placebo for CIVI 007 will be commercially available sterile saline for injection. An unblinded pharmacist will prepare the study drug for blinded administration by the investigator site as detailed in the protocol's Pharmacy Manual.

Dosing is to be in the morning following an overnight fast:

- CIVI 007 is to be administered SC into the abdomen (or thigh or upper arm, if necessary) from a solution at 150 mg/mL.
- Doses of CIVI 007 are comma Q4W x2, comma on Day 1 followed by comma on Day 29 and comma Q4W x2.
- Placebo is to be administered SC into the abdomen (or in thigh or upper arm, if necessary) on Day 1 and Day 29. The volume of injection will be randomly assigned to match the active CIVI 007 dose.

#### 2.2.4 Sample Size Determination

Approximately 48 patients (12 patients per active treatment group, 12 patients per placebo treatment) will be randomized into 1 of 4 treatment groups.

The sample size chosen for this study was not based on power calculations. However, the number of patients in each part of the present study is common in early clinical studies and is considered sufficient to achieve the objectives of the study without exposing undue numbers of patients to study drug.

# 2.3 Study Endpoints

# 2.3.1 Primary Safety/Tolerability Endpoints

The primary safety/tolerability endpoints for this study are as follows:

· incidence and severity of any drug-related AE

 incidence of clinically significant laboratory abnormalities, based on drug-induced changes from baseline in haematology, clinical safety chemistry, and urinalysis test results.

#### 2.3.2 Secondary Endpoints

The secondary efficacy endpoints include the following changes from baseline measured approximately 28 days after the first and 28 and 56 days after the last injection of study drug:

The percent change in PCSK9 and LDL-C

#### 2.3.3 Exploratory Endpoints

The exploratory endpoints include the following:

#### 2.3.3.1 Lipid/Pharmacodynamic (PD) Endpoints

PD endpoints are the absolute and % changes from baseline (except where indicated) in the levels of the following in serum or plasma over the time course of the treatment period and follow-up:

- PCSK9 (absolute only)
- LDL-C (absolute only)
- VLDL-C
- triglycerides
- HDL-C
- Non-HDL-C
- total cholesterol
- lipoprotein (a)
- apolipoproteins B and A-I
- hsCRP

## 2.3.3.2 Pharmacokinetic (PK) Endpoints

The following PK parameters will be calculated for CIVI 007, where possible:

- Cmax
- time of the maximum observed plasma concentration (Tmax)
- AUC0-t
- concentration observed at pre-dose (Ctrough) (Day 29 only)

Additional exploratory PK parameters, which may include but are not limited to the following, may be calculated:

- area under the plasma concentration-time curve from time 0 extrapolated to infinity (AUC0-∞)
- area under the plasma concentration-time curve from time 0 to 168 hours (AUC0-168)

- percentage of AUC0-∞ that is due to extrapolation (%AUCextrap)
- apparent terminal elimination rate constant (λz)
- apparent plasma terminal elimination half-life (t1/2)
- apparent total plasma clearance (CL/F)
- apparent volume of distribution during the terminal phase (Vz/F)

# 2.3.4 Safety Variables

The safety variables include adverse events, safety laboratory parameters (including clinical safety chemistry, hematology, coagulation parameters including fibrinogen, complement activation, cytokines and urinalysis), 12-lead ECGs, physical examinations, and vital signs. Samples will also be collected for the potential future assessment of anti-drug antibodies.

# 3 STATISTICAL METHODOLOGY

# 3.1 General Considerations

# 3.1.1 Analysis Day

Analysis day will be calculated from the date of first dose of study drug. The day of the first dose of study drug will be Day 1, and the day immediately before Day 1 will be Day -1. There will be no Day 0.

#### 3.1.2 Analysis Visits

Scheduled visits will be assigned to analysis visits as recorded on the case report form (CRF). Unscheduled and early termination visits will be assigned to analysis visits according to the following visit windows:

Analysis Visit	Target Analysis Day	Low Analysis Day	High Analysis Day
Day 8	8	2	11
Day 15	15	12	18
Day 22	22	19	25
Day 29	29	26	32
Day 36	36	33	39
Day 43	43	40	46
Day 57	57	47	71
Day 85	85	72	85 or End of Study (if Last
			Observation > Day 85)

Within an analysis visit window, the measurement from the visit closest to the defined target analysis day will be used. If there is more than one measurement with equal distance to the defined target analysis day, the latter will be used. If no visits occur within a visit window, the measurement for this visit will be treated as missing.

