The Follow-up Period then begins and patients will attend scheduled follow-up visits at Days 36, 43, 57 and 85 to assess safety, tolerability, PK, and PD. The duration of the Follow-up Period will therefore be approximately 2 months from the last dose of study drug, unless extended follow-up is required based on Day 85 LDL-C assessments or other Investigator determined safety considerations.

[figure not shown]
Extended follow-up visits will be conducted on a monthly basis for up to 3 months if Day 85 LDL-C levels are <80% of their baseline level; extended follow-up will end within the 3-month period if LDL-C levels are ≥80% of baseline. Extended follow-up visits (frequency and assessments will be at the discretion of the Investigator) to monitor Investigator determined safety considerations may extend beyond 3 months, if deemed appropriate by the Investigator, and will continue until there are no safety observations requiring further follow-up. The total duration of

the study for each patient will be approximately 3 to 6.5 months, depending on the variable length of the screening, and follow up periods.

A Safety Review Committee (SRC) will perform interim unblinded reviews of safety, tolerability, and available PK and PD data collected for the purposes of protecting subject safety as well as providing guidance to the Sponsor on the evolving clinical profile of CIVI 007. The SRC will comprise, at a minimum, the Sponsor's clinical development contact, the study Medical Monitor, a gastroenterologist not involved in study conduct and a pharmacokineticist. A separate document will detail the SRC's operating procedures.

The study design is graphically summarized in Figure 1:

Figure 1. Summary of the Study Design

Mo = month; Q4W = Every 4 weeks; Wk = week; R = randomization;

A visit window of ± 3 days will be permitted for each study visit except for the first day of study drug administration.

Appendices A and B define the detailed Schedule of Procedures and Clinical Laboratory Analyte measures, respectively, to be performed during the study.

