8.1 Individual Patient Safety Monitoring and Criteria For Discontinuation of Study Drug

When any the following criteria are met, patients will be monitored for safety and discontinuation of study drug considered using the following guidance.

- Liver (as per FDA guidance on drug-induced liver injury 16)
 - Patients with signs or symptoms consistent with liver injury (such as nausea, vomiting, anorexia, fatigue, right upper abdominal pain or discomfort) should undergo immediate testing of ALT, AST, GGT, bilirubin, ALP, PT, and INR.
 - In the absence of clinical symptoms, patients with ALT or AST > 3xULN (if normal at baseline) or >2-fold change (if abnormal at baseline) should be retested within 48 to 72 hours for the usual serum measures (ALT, AST, ALP, and bilirubin) to confirm the abnormalities and to determine if they are increasing or decreasing. There also should be inquiry made about symptoms at the time of follow-up.
 - If the above abnormalities are confirmed,
 - repeat liver enzyme and serum bilirubin tests two or three times weekly. The frequency of retesting can decrease to once a week or less if abnormalities stabilize or the study drug has been discontinued and the patient is asymptomatic.
 - Obtain a more detailed history of symptoms and prior or concurrent diseases.
 - Obtain a history of concomitant drug use (including nonprescription medications and herbal and dietary supplement preparations), alcohol use, recreational drug use, and special diets.
 - Rule out acute viral hepatitis types A, B, C, D, and E; autoimmune or alcoholic hepatitis; NASH; hypoxic/ischemic hepatopathy; and biliary tract disease.
 - Obtain a history of exposure to environmental chemical agents.
 - Obtain additional tests to evaluate liver function, as appropriate (e.g., INR, direct bilirubin).
 - Considering gastroenterology or hepatology consultations.
 - Study drug discontinuation should occur if:
 - ALT or AST >8xULN
 - ALT or AST >5xULN for more than 2 weeks
 - ALT or AST >3xULN and (bilirubin >2xULN or INR >1.5)
 - ALT or AST >3xULN with the appearance of fatigue, nausea, vomiting, right upper quadrant pain or tenderness, fever, rash, and/or eosinophilia (>5%)
- Platelet Count

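### The Day 29 windowing rule gives the scheduled value no priority and does not exclude values taken after the second injection

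*SAP*

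**What the plan says.** SAP 3.1.2 assigns scheduled visits by their CRF label. For the rest it states: "Unscheduled and early termination visits will be assigned to analysis visits according to the following visit windows". The Day 29 row has target 29, low 26 and high 32. Selection then follows one sentence, "Within an analysis visit window, the measurement from the visit closest to the defined target analysis day will be used", and a tie rule, "If there is more than one measurement with equal distance to the defined target analysis day, the latter will be used".

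Three other places bear on this:

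- Protocol 3.1 gives the second injection at the Day 29 visit and adds: "A visit window of ± 3 days will be permitted for each study visit except for the first day of study drug administration". The Day 29 visit, and the injection with it, may therefore fall on Days 26 to 32.
- SAP 3.4.1 uses the Day 29 value of LDL-C and PCSK9 for the secondary endpoint about 28 days after the first injection.
- SAP 3.1.3 defines baseline as the last scheduled value before the first dose. It thus states both a preference for scheduled values and a pre-dose condition. SAP 3.1.2 states neither for Day 29.

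**The concern.** The Day 29 result is meant to describe the effect of the first injection alone. The analysis window extends beyond the injection whenever the visit falls before Day 32, and the selection rule looks only at distance from Day 29. Read literally, it can pass over the scheduled pre-dose value for one taken after the second dose.

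Protocol 5.2 says lipid reductions begin within one week of dosing, so a value a few days after the second injection may already carry some of its effect. The point is sharpest in Group 2, where the second dose differs from the first: a post-injection value there no longer reflects the first dose level alone. With 12 patients per arm, one such value has weight 1/12, about 8%, in an arm mean.

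There is also a reproducibility issue. Two programmers working from 3.1.2 could derive different Day 29 datasets.

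**Working it through.** The SAP gives no figure to reproduce here, so the check is to enumerate the rule.

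**Inputs.** Target T = 29 and window 26 to 32 (SAP 3.1.2); scheduled visit and second injection on day s = 26 to 32 (Protocol 3.1); a later unscheduled or early-termination visit on day u = s+1 to 32.

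**Rule.** With a scheduled value present, the later value is chosen if |u − 29| < |s − 29|, or on equality through the tie rule.

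| Injection day s | Distance of s | Later days in window | Nearer | Tie (later used) | Displaced |
|---|---|---|---|---|---|
| 26 | 3 | 27-32 | 27, 28, 29, 30, 31 | 32 | 6 of 6 |
| 27 | 2 | 28-32 | 28, 29, 30 | 31 | 4 of 5 |
| 28 | 1 | 29-32 | 29 | 30 | 2 of 4 |
| 29 | 0 | 30-32 | none | none | 0 of 3 |
| 30 | 1 | 31-32 | none | none | 0 of 2 |
| 31 | 2 | 32 | none | none | 0 of 1 |
| 32 | 3 | none | none | none | 0 of 0 |

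Total: 6 + 4 + 2 = 12 of 6 + 5 + 4 + 3 + 2 + 1 = 21 pairings. Displacement on a later day needs an early visit, on Days 26 to 28.

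**Scheduled value missing.** The distance comparison no longer protects the slot. Any post-injection value up to Day 32 can then fill it, whatever the injection day.

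**Documented route for LDL-C and PCSK9.** Protocol 6.5 has all Day 85 procedures, including the fasting lipid panel and PCSK9, done at early termination, and SAP 3.1.2 places that visit by window. Example: second injection on Day 27, early termination on Day 30. The distances are |27 − 29| = 2 and |30 − 29| = 1, so the Day 30 value is reported as Day 29.

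**Documented route for liver tests.** Protocol 8.1 says asymptomatic patients above its ALT/AST thresholds "should be retested within 48 to 72 hours" for ALT, AST, ALP and bilirubin. Counting the 48 to 72 hours from the visit (an assumption):

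- visit on Day 26, retest on Day 28 (1 against 3) or Day 29 (0 against 3): displaced;
- visit on Day 27, retest on Day 29 (0 against 2) or Day 30 (1 against 2): displaced;
- visit on Day 28, retest on Day 30 (1 against 1, tie): displaced; on Day 31 (2 against 1): not displaced;
- visit on Day 29, retest on Day 31 or 32: not displaced.

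**After the change.** With priority for the scheduled value, the count is 0 of 21 whenever that value exists. If post-injection values are also barred from Day 29, it is 0 when the scheduled value is missing as well.

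**The case against.** The best defence is that the rule is narrower than it looks. Scheduled visits are placed by CRF label, the windows are introduced only for unscheduled and early-termination visits, and the selection sentence speaks of choosing within a window. It could therefore apply only among windowed visits, with the scheduled value implicitly first. SAP 5 also leaves detailed programming specifications to a separate document. This reading is possible, but it leaves no rule for choosing between a scheduled and an unscheduled value at the same analysis visit. It also does not bar a post-injection value when the scheduled one is missing.

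The defence is right that the efficacy exposure is small. Sites are blinded to lipids after randomization (Protocol 5.3), so lipid results give them no reason to repeat a panel, and the liver retest does not include LDL-C or PCSK9.

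A reader might infer more than the documents support:

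- *That the 3 h and 8 h samples on Day 29 tie with the pre-dose sample and win.* They are planned timepoints within one visit, and the rule compares visits. SAP 3.5.2 gives the PK samples separate time windows, and lipids, PCSK9 and safety chemistry have no planned 3 h or 8 h sample.
- *That the primary laboratory endpoint is distorted.* SAP 3.6.2 summarizes the incidence of abnormalities, with CTCAE grades for selected parameters. Nothing limits that incidence to the windowed value. What is exposed is the by-visit summary.
- *That the open-ended Day 85 window has the same effect.* Monthly extended visits lie further from Day 85 than a scheduled visit within ±3 days, so they cannot displace it. The LDL-C-driven extension itself presupposes a Day 85 LDL-C result.

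**Conclusion.** The gap is real but minor. As written, SAP 3.1.2 allows a value taken after the second injection to be reported as Day 29, either by displacing the scheduled value when the visit falls on Days 26 to 28 or by filling the slot when that value is missing.

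The 12 of 21 shows how far the rule reaches and should not be read as a frequency. The documents give no rate of unscheduled or early-termination visits and no distribution of actual visit days, and the Group 2 doses are redacted, so neither the frequency nor the bias can be estimated. On the documented routes it should be rare: early termination within days of dose 2 for LDL-C and PCSK9, and the liver retest for ALT, AST, ALP and bilirubin.

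The conclusion rests on the literal text of 3.1.2. If the programming specifications already give scheduled values priority, the displacement part falls away, but the missing-value part remains unless they also impose a pre-injection condition.

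**What to change.** Add to SAP 3.1.2, before database lock:

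1. The scheduled-visit value takes precedence; unscheduled or early-termination values are used for an analysis visit only if the scheduled value is missing.
2. In patients who receive the second injection, only values taken before it qualify for Day 29.
3. Post-injection values in the Day 26 to 32 window stay in the listings and abnormality-incidence tables. They are not assigned to Day 29 and are not moved to Day 36.

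The last clause matters. Day 36 has its own window of Days 33 to 39, and moving a value taken perhaps one day after the injection into it would create a new timing error if the scheduled Day 36 value were missing. Since these values would then belong to no analysis visit, the SAP should also say whether LOCF may draw on them for Day 57 and Day 85.

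The cost is a few sentences and a small change to the derivation. No data collection, visit or sample changes.
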